#### 4.2 SCIENTIFIC RATIONALE FOR STUDY DESIGN

A placebo control is the gold standard clinical trial design appropriate for conditions without any approved treatments so that variability in the disease can be assessed. The use of vehicle of AG-86893 has the potential to provide some relief to the participant because of actions similar to an artificial tear, lubricating the ocular surface and reducing irritation. However, the alternative of an open-label study without a control group introduces too many biases.

It is essential to investigate the dose-response of the proposed treatment in order to select a dose for further study to confirm any potential treatment effects.

#### 4.3 JUSTIFICATION FOR DOSE

The doses selected in this study were based on the doses that were found to be effective in inhibiting new blood vessel growth on the cornea in a rabbit model. In that study, doses of 0.1%, 0.3%, and 1% were equally effective in inhibiting the blood vessel growth caused by suture placement. Rabbits dosed QID bilaterally for 7 days at doses of 0.3%, 0.6%, and 1% showed no signs of discomfort or ocular irritation. These doses were tested for safety and ocular histopathology in a 28-day GLP rabbit and monkey study after topical TID dosing of AG-86893. All the doses tested were safe and 1% identified as the NOAEL (no-observed-adverse-effect-level) dose. It is therefore expected that the doses of 0.1% and 0.3% administered TID will be tolerable and safe, and that at least 1 concentration will be effective in reducing hyperemia in participants with pterygium.

#### 4.4 END OF STUDY DEFINITION

A participant is considered to have completed the study if he or she has completed all phases of the study, including the last visit or the last scheduled procedure shown in the Schedule of Assessments ([Section 1.3](#)). Furthermore, the study will be completed when all participant's images have been assessed by central reading center.

### 5 STUDY POPULATION

#### 5.1 INCLUSION CRITERIA

In order to be eligible to participate in this study, an individual must meet all of the following criteria:

1. Signed an IRB-/IEC-approved informed consent form (ICF) prior to any study-specific procedures

2. Willingness to comply with the study procedures and study drug administration and to return for all study visits
3. Male or female, 18 years of age or older
4. Body mass index between 18 and 38 kg/m^2, inclusive
5. Females of childbearing potential must have a negative pregnancy test at baseline and must be on established, adequate contraception (e.g., oral contraceptive or bilateral tubal ligation) and males must use condoms if their partner is of childbearing potential and their female partner should also use an additional effective means of contraception (e.g., oral contraceptive or bilateral tubal ligation), or they must agree to abstain from sexual intercourse with a female partner for the duration of the study; contraception should be continued for 3 months after the last dose. Females of non-reproductive potential are permitted to enter the study without the need for a pregnancy test. Non-reproductive potential is defined as one or more of the following: (1) women who are postmenopausal ( $\geq 47$  years of age who have been amenorrheic for at least 12 consecutive months), (2) women who do not possess a uterus (e.g., previous hysterectomy), (3) women who do not possess both ovaries (e.g., previous bilateral oophorectomy), and (4) women with a bilateral tubal ligation
6. Good health with no clinically significant findings based on the medical history, ECG, vital signs, blood chemistry, hematology, and urinalysis findings, as determined by the investigator. Abnormal laboratory results must be determined as not clinically significant by the investigator
7. Presence of pterygium, extending beyond the limbus, with associated conjunctival hyperemia in the quadrant containing the pterygium of grade  $\geq 2$  at screening, as assessed by the central reading center based on ocular photography using a 5-point scale of 0 = none, 1 = mild, 2 = moderate, 3 = severe, and 4 = very severe, AND a conjunctival hyperemia score of  $\geq 1$  in at least 2 of the remaining quadrants of the same eye at screening (study eye). If both eyes are affected and meet the inclusion criteria, the eye with the higher overall hyperemia score will be used as the study eye. If both eyes are eligible and have the same hyperemia score, the right eye will be selected as the default study eye

## 5.2 EXCLUSION CRITERIA

In order to be eligible to participate in this study, an individual must not meet any of the following criteria:

### Ocular criteria

- a) BCVA in either eye of 35 ETDRS letters or worse (Snellen equivalent of 20/200) at screening or baseline
- b) History or presence of any ocular diseases other than pterygium or its sequelae, including neoplasia
- c) Diagnosis of ocular hypertension or glaucoma requiring use of intraocular pressure (IOP)-lowering medication
- d) Use of contact lenses during the study in the study eye
- e) Aphakia or torn posterior capsule in the study eye
- f) History or evidence of the following surgeries in the study eye at any time, unless specified:
  - a. Pterygium removal
  - b. Corneal transplant

- c. Glaucoma surgery, shunt, or microstent
  - d. Refractive surgery
  - e. Surgery on ocular muscles
  - f. Any retinal surgery
  - g. Cataract surgery within 3 months or yttrium aluminium garnet (YAG) capsulotomy within 1 month prior to baseline
- g) Current use of any ophthalmic medications in the study eye other than artificial tears or ocular decongestants; ocular decongestants must be washed out for a minimum of 7 days prior to baseline and use is prohibited 2 days before any study visit
- h) History of any intravitreal, subconjunctival medication in the study eye within 12 months prior to baseline

#### Non-ocular criteria

1. Presence of a non-healing/oversize wound, ulcer, or fracture
2. Inadequate liver function, as demonstrated by total bilirubin  $>1.5 \times$  upper limit of normal (ULN) at screening (unless participant has a documented history of Gilbert's syndrome), aspartate transaminase (AST) and alanine transaminase (ALT)  $\geq 2.5 \times$  ULN or serum albumin  $<3.5$  g/dL
3. Any malignancy other than adequately treated nonmelanomatous skin cancer, or adequately treated prostate cancer in men over the age of 70
4. Any uncontrolled systemic disease, including cardiac disease; hypertension; diabetes mellitus; mental, neurological, respiratory, gastrointestinal, renal, or hepatic dysfunction; infectious disease; or malignancy
5. Use of any immunosuppressive therapy during the study
6. Use of marijuana during the study or within 2 days prior to screening
7. Any disease or condition that the medical monitor or the investigator believes will impact the participant's ability to adhere to the study schedule or may confound the results
8. Participation in any investigational study within 30 days prior to baseline or exposure to an investigational drug must be fully washed out (at least 5 half-lives)
9. Donation of  $\geq 450$  mL (e.g., 1 unit) of blood or blood products within 56 days prior to baseline (for participants participating in the plasma concentration blood draw), or plans to donate blood during the study (all participants)
10. Pregnancy, plans for pregnancy, or breastfeeding during the study
11. History of active alcohol or substance abuse as defined by Diagnostic and Statistical Manual of Mental Disorders, Fifth Edition (DSM V) criteria

### 5.3 LIFESTYLE CONSIDERATIONS

Not applicable.

### 5.4 SCREEN FAILURES

Screen failures are defined as participants who consent to participate in the clinical trial but are not assigned to the study intervention or entered into the study. A set of screen failure information is

required to ensure transparent reporting of screen failure participants, to meet the Consolidated Standards of Reporting Trials (CONSORT) publishing requirements, and to respond to queries from regulatory authorities. This information includes participants' demographic information, screen failure details, eligibility criteria, and any SAEs.

In some cases, individuals who do not meet the criteria for participation in this trial (screen failure) may be rescreened (e.g., a hypertensive individual with high blood pressure due to missed medication on the day of the screening visit, or an individual willing to discontinue use of ocular decongestants for the duration of the study). Rescreened participants should be assigned the same participant number as for the initial screening.

## 5.5 STRATEGIES FOR RECRUITMENT AND RETENTION

Sites will recruit participants from their database as well as locally. Any advertisement must be approved by the IRB/IEC. Refer to the Manual of Procedures (MOP) for additional information.

## 6 STUDY INTERVENTION

### 6.1 STUDY INTERVENTIONS ADMINISTRATION

#### 6.1.1 STUDY INTERVENTIONS DESCRIPTION

The active study treatment will be the investigational agent AG-86893, which is a topical ophthalmic nanosuspension formulation of nintedanib (Ofev®, Boehringer Ingelheim), delivered at concentrations of either 0.1% or 0.3%, depending on randomized treatment assignment. The control treatment will be AG-86893 vehicle. All 3 study interventions will be delivered to the study eye as a single eye drop TID, using the provided white, opaque, low-density polyethylene (LDPE) eye dropper bottle.

#### 6.1.2 DOSING AND ADMINISTRATION

Once study entry procedures have been completed (see [Section 4.1](#)), the independent drug administrator not affiliated with the assessment of the participant will obtain the randomization assignment and drug kit number from the Interactive Web Response System (IWRS). The independent (unmasked) drug administrator will vigorously shake the eye dropper bottle for 10 seconds prior to administration to the study eye.

A single eye drop (~40 µL eye drop) of AG-86893 or AG-86893 vehicle control will be applied TID (morning, afternoon, and evening, approximately 8 hours apart) to the study eye until the Day 28 visit. A single study treatment will be administered to each participant in this study by the independent drug administrator on the morning of the clinic visits on Day 1 and Day 28. The participant will be instructed on Day 1 how to self-dose using the eye dropper bottle for the remaining doses with written instructions provided on a participant dosing diary. Two bottles of AG-86893 or vehicle will be provided to each participant at Day 1; participants will be instructed to bring both of these bottles with them when they return to the clinic for the Day 7 (optional) and Day 28 visits, or to any unscheduled visits during this period. Participants will be required to remain in the clinic for assessment of Adverse Events for at least 1 hour after the first administration on Visit 1 (V1D1).

Study drug should be consistently dosed approximately 8 hours apart on each day (e.g., at 07:00, 15:00, and 23:00). Specific instructions for participants to self-dose are provided in the MOP, including instruction that in the event of a forgotten/delayed dose, the delayed dose is to be skipped if there is less than 2 hours until the next scheduled dose.

### 6.2 PREPARATION/HANDLING/STORAGE/ACCOUNTABILITY

#### 6.2.1 ACQUISITION AND ACCOUNTABILITY

The investigator designee or independent drug administrator (not directly involved in the assessment of study participants) must keep an accurate accounting of the number of investigational units received from Allgenosis, and the number of units returned to Allgenosis or designee during and at the completion of the study. A detailed inventory must be completed for the study drug.

The used study bottles from each participant will be weighed at the Day 7 (if conducted in-clinic) and Day 28 visits to estimate compliance; weight will be recorded on the electronic Case Report Form (eCRF). Participants will be reminded to return both of their study bottles at the Day 28 visit.

All clinical study drug and/or supplies will be returned to Allgenosis or its designee for destruction.

---

### 6.2.2 FORMULATION, APPEARANCE, PACKAGING, AND LABELING

AG-86893 is a topical ophthalmic nanosuspension formulation of nintedanib. AG-86893 is yellowish, while AG-86893 vehicle is clear.

Each active study treatment bottle contains AG-86893 (~5 mg or 15 mg), tyloxapol, hypromellose (HPMC), benzalkonium chloride, sodium chloride, ethylenediaminetetraacetic acid (EDTA) disodium, monobasic potassium phosphate, and sodium hydroxide, at pH 7.0.

Each control treatment bottle contains AG-86893 vehicle, which contains tyloxapol, HPMC, benzalkonium chloride, sodium chloride, EDTA disodium, monobasic potassium phosphate, and sodium hydroxide, at pH 7.0.

AG-86893 and AG-86893 vehicle will be packaged in white, 5-mL LDPE ophthalmic bottles and supplied by Allgenesis or designee. Study medication will be provided in 2 separate bottles. All study medications will be labeled with the protocol number and medication kit numbers. The label will also specify the storage conditions (room temperature) and state that the study medication is limited to investigational use.

---

### 6.2.3 PRODUCT STORAGE AND STABILITY

The study drug must be stored at room temperature (15° – 30°C). Temperature will be monitored while stored at sites, and participants in the P2-86893-001 trial will be instructed not to expose the product to refrigerated or frozen temperatures, and that bottles should be protected from direct sunlight.

---

### 6.2.4 PREPARATION

Not applicable.

## 6.3 MEASURES TO MINIMIZE BIAS: RANDOMIZATION AND MASKING

Prior to initiation of study treatment, randomization will occur by site personnel via the IVRS or IWRS once it is confirmed that the participant meets the final study entry criteria (see [Section 4.1](#)). The IVRS/IWRS will provide the participant identification number used on all study documents and will be used to manage the randomization and treatment assignment based on a central randomization scheme prepared by Trial Runners. Study drug will be labeled with medication kit numbers, and the IVRS/IWRS will provide each site with the specific medication kit number(s) for each randomized participant at the time of randomization. Sites will dispense study drug according to the IVRS/IWRS instructions. Sites will receive the IVRS/IWRS confirmation notifications for each transaction. All notifications are to be maintained with the study source documents.

To prevent possible unmasking, access to study drug kits will be limited to staff not involved in the care and evaluation of participants or the handling of data throughout the study. To maintain the double mask, an independent drug administrator not affiliated with the care of the participant will apply the single eye drop to the participant at the Day 1 and Day 28 visits. Since AG-86893 and vehicle are different colors, it will be important to advise the participant to not discuss what the medication looks like. In addition, when the used study medication is returned at the Day 28 visit (2 bottles per participant), the unmasked drug administrator should be responsible for collecting and weighing the bottles.

Masking of individual participant treatment assignments will be maintained throughout the study for all participants and required site personnel until the database is locked for the final analysis. If it is necessary for the safety and appropriate treatment of a participant, the treatment assignment can be unmasked by the site via the IVRS/IWRS. When possible, the medical monitor should be notified prior to the unmasking, and the reason for breaking the mask will be documented in the source documentation. The investigator should inform the medical monitor of the unmasking if there is no notification prior to the unmasking. The treatment assignment for the participant can be determined by designated site personnel calling into the IVRS/IWRS via password-protected access. The reason for breaking the code should be recorded in the participant's source documents.

#### 6.4 STUDY INTERVENTION COMPLIANCE

Participants who are inadvertently enrolled, despite significant deviation from protocol-specified inclusion/exclusion criteria, will be discontinued from participation in the study. Participants will be scheduled for follow-up visits and followed for 8 weeks post-treatment for safety per protocol.

At each post-baseline visit, participants will be questioned as to concomitant medications, as well as exclusionary criteria to ensure protocol compliance. Urine drug screens will be performed during the screening visit (Day -14 to Day -2), at the Days 7 (if conducted in-clinic), 28, and 84 visits for all participants. Dosing compliance will be assessed when the participant returns the study drug (both bottles) to the investigator, at which time the study drug bottles will be weighed.

#### 6.5 CONCOMITANT THERAPY

Ocular medications, other than artificial tears and ocular decongestants, are prohibited. Ocular decongestants must be washed out for a minimum of 7 days prior to baseline and use is prohibited 2 days before any study visit. Topical drops for examination procedures, such as anesthetics, dilating agents, fluorescein and lissamine green, are permitted.

Systemic medications that may interfere or confound the evaluation of conjunctival hyperemia are prohibited and should be washed out in the 7 days prior to baseline. Washout should not commence until after written informed consent has been obtained. Refer to the MOP for examples of prohibited medications.

Participants will be instructed on all study procedures and requirements as appropriate. Participants will be instructed on use of permissible topical eye drops and on prohibited medications.

Medication considered necessary for the participant's welfare may be given at the discretion of the investigator. Participants should be instructed to maintain a stable dose of chronic medications during the study whenever possible. All concurrent medications (prescription, over-the-counter and supplements), adjunct therapies, and concurrent procedures will be recorded on the appropriate eCRF page.

The decision to administer a prohibited medication/treatment is done with the safety of the study participant as the primary consideration. Whenever possible, the medical monitor should be notified before the prohibited medication/treatment is administered.

---

##### 6.5.1 RESCUE MEDICINE

As there is no pharmacologic treatment for pterygium, no rescue medication is proposed in this study. Investigators may direct participants to the use of eye drops (e.g., artificial tears, decongestant drops, etc.) as appropriate, to alleviate any symptoms related to the participant's condition.

## 7 STUDY INTERVENTION DISCONTINUATION AND PARTICIPANT DISCONTINUATION/WITHDRAWAL

### 7.1 DISCONTINUATION OF STUDY INTERVENTION

The investigator may discontinue the study drug at any time if there is a safety concern. If the study drug is discontinued, then the participant will early exit from the study. If the participant has discontinued the study drug because of an SAE related to the study drug, that participant should be monitored for at least 30 days or until the SAE has resolved or stabilized.

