### 7.2 PARTICIPANT DISCONTINUATION/WITHDRAWAL FROM THE STUDY

Participants are free to discontinue the study at any time, for any reason, and without prejudice to further treatment. The investigator may remove a participant if, in the investigator's judgment, continued participation would pose unacceptable risk to the participant or to the integrity of the study data. Reasons for removal or withdrawal might include:

- Withdrawal of consent
- Administrative decision by the investigator or Sponsor
- Significant protocol deviation
- Participant noncompliance, or other significant protocol deviation
- Safety concern by the investigator or Sponsor
- Lost to follow-up

With the exception of withdrawal of consent, participant withdrawal should be discussed with the Medical Monitor, when possible, prior to withdrawing. Notification of early participant discontinuation from the study and the reason for discontinuation will be made to Allgenesis and will be clearly documented on the appropriate eCRF. If a participant discontinues prior to completing the study, the procedures outlined for the Exit visit should be performed at the last visit the participant attends.

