### 8.3.7 TIME PERIOD AND FREQUENCY FOR EVENT ASSESSMENT AND FOLLOW-UP

Any medical condition that is present at the time that the participant is screened will be considered as medical history and not reported as an AE. However, if the study participant's condition deteriorates at any time after the time of Informed Consent, it will be recorded as an AE.

Changes in the severity of an AE will be documented in the source and eCRF to allow an assessment of the duration of the event at each level of severity to be performed. The AE will be recorded in the CRF under the highest level of severity achieved; i.e. if an event progresses from mild to moderate, the severity of the AE will be changed in the CRF, but the date of onset will remain unchanged. Adverse events characterized as intermittent require documentation of onset and duration of each episode.

The collection of AEs and SAEs will commence from the time the Informed Consent Form is signed and continue until the last day of study participation (D84). Events will be followed for outcome information until resolution or stabilization during the study or continue until 7 days (for non-serious AEs) or 30 days (for SAEs) after the last day of study participation (D84).

Adverse events will be monitored throughout the study beginning at the time of Informed Consent. After the first administration of AG-86893, participants will be observed for AEs by remaining in the clinic until at least 1 hour after dosing. At this 1 hour post-initial dose timepoint, and at each post-screening visit, the investigator will begin by querying for AEs by asking each participant a general, non-directed question, such as "How have you been feeling since the last visit?" Directed questioning and examination will then be done as appropriate. All reported AEs will be documented on the appropriate eCRF, including seriousness, severity, relationship to study drug, action taken, and outcome (including date of resolution or stabilization, if AE is not ongoing). If AEs occur, the first concern will be the safety of the study participants.

---

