### 8.3.9 SERIOUS ADVERSE EVENT REPORTING

Any SAE occurring during the study period should be immediately (i.e., within 24 hours of learning of the event) reported via the Trial Runners SAE email address listed on the protocol page iii. The SAE is recorded on the appropriate eCRFs. In the event of an early termination within the first 4 weeks after study drug administration, the occurrence of an SAE within 8 weeks from Baseline/Day 1 should be reported immediately to Trial Runners personnel. All participants with an SAE that is related to study drug must be followed for at least 30 days and the outcomes reported until the event is resolved or stabilized. The investigator should supply the sponsor and the HREC/IRB/IEC with any additional requested information (e.g., autopsy reports and terminal medical reports).

In the event of an SAE, the investigator must:

- Notify the Trial Runners safety office and the medical monitor immediately by email using the SAE reporting forms provided by Trial Runners (see page iv of the protocol for the SAE email address). A fax number will be provided for reporting in the event internet access is unavailable during the required reporting period. Emergency phone numbers and relevant personnel contacts are also on page iii of the protocol
- Obtain and maintain in the participant's files all pertinent medical records, information, and medical judgments from colleagues who assisted in the treatment and follow-up of the participant
- Provide Allgenensis with a complete, written case history (SAE report form) which includes a statement as to whether the event was or was not related to the use of the investigational drug
- Promptly inform the governing HREC/IRB/IEC of the SAE if it is drug-related. For other SAEs, notify the governing HREC/IRB/IEC as required by the HREC/IRB/IEC, local regulations, and the governing health authorities

Adverse drug reactions that are both serious and unexpected (suspected unexpected serious adverse reactions [SUSARs]) will be subject to expedited reporting by the Sponsor to HREC and TGA as required by the relevant regulations. TGA reporting must occur within 15 calendar days of first knowledge, or for fatal or life-threatening events, an initial or full report must be made within 7 calendar days and a follow-up report must be made, if necessary, within the 15-calendar day timeframe.

---

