3.7 Adverse Events

Any unfavorable and unintended medically significant changes in vital sign (including an abnormal laboratory finding), symptom, or disease after the time of signing the consent form, whether or not related to the study eye drops, will also be recorded as an adverse event (AE). An AE that results in any of the following outcomes is considered a serious adverse event (SAE):

- Death
- Life-threatening AE

- Inpatient hospitalization or prolongation of existing hospitalization
- Persistent or significant disability/incapacity
- Congenital anomaly/birth defect

Worsening of the pterygium is not an AE, unless the lesion growth is greater than expected.

The following information will be collected and tabulated for all AEs:

- Verbatim description
- Date of Onset
- Date of Resolution, or Stabilization, or Ongoing
- Severity (Mild, Moderate, Severe)
- Relationship to Study Intervention (Not related, Unlikely related, Possibly related, Related)
- Action taken against study intervention (None, Study eye drop interrupted, or withdrawn)
- Outcome (Recovered/Resolved, recovered/Resolved w/Sequela, Recovering/Resolving, Not Recovered/Not Resolved, Fatal, Unknown)
- Whether the AE led to study discontinuation
- Whether or not a concomitant medication or procedure was required
- Classified as a serious adverse event (SAE) or not
- SAE Code (Death, Life-threatening, Inpatient, or prolonged hospitalization, Persistent or significant disability/incapacity, Congenital anomaly or birth defect, Other medically important event)

The collection of AEs and SAEs will commence from the time the Informed Consent Form is signed and continue until the last day of study participation (Day 84). Events will be followed for outcome information until resolution or stabilization during the study or continue until **7 days** (for non-serious AEs) or **30 days** (for SAEs) after the last day of study participation (Day 84).

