4.7.1 Events of Special Interest

The following events of special interest will be monitored and may trigger an IDMC meeting, as well as may trigger study treatment interruption.

Abnormal liver function test results:

- ALT or AST >8x ULN
- ALT or AST >5x ULN for more than 2 weeks
- ALT or AST >3x ULN and (total bilirubin >2x ULN or International Normalized Ratio [INR] >1.5)
- ALT or AST >3x ULN with the appearance of worsening of fatigue, nausea, vomiting, right upper quadrant pain or tenderness, fever, rash, or eosinophilia
- Any other safety signals observed during routine data review that warrant convening of the IDMC, in the opinion of the Medical Monitor

Special ocular events:

- Ocular inflammation, including iritis and uveitis
- ≥ 2 grade increase in corneal edema, corneal staining or edema
- ≥ 2 grade increase in any cataract
- IOP change of ± 7 mmHg from baseline
- Loss of 15 letters or more BCVA

For each type of AE reported, the number and percent of participants will be tabulated based on the preferred term. The tables will be generated by relationship to treatment as well as by system organ class and severity, for treatment-emergent AEs, as well as pre-treatment AEs (occurring prior to first dose) and post-treatment AEs (occurring 3 days after the last dose).

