6.2.3 Treatment Discontinuation and Rescue Medications

As there is no pharmacologic treatment for pterygium, no rescue medication is proposed in this study. Therefore, no switch treatment will be considered. The participant will be exited from the study after discontinuation from the study treatment. Investigators may direct participants to the use of eye drops (e.g., artificial tears, decongestant drops, etc.) as appropriate, to alleviate any symptoms related to the participant's condition.

Efficacy assessment collected from the treatment discontinuation exit will be mapped to the next scheduled visit and considered as observed data. (i.e., the mapping will be performed prior to any data imputation if any).

Safety assessment for the treatment discontinuation exit will not be mapped. Instead, it will be treated as the last assessment during treatment period.

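### Anyone who stops study drug is exited from the study, and no scheduled contact then looks for new adverse events in an ordinary early stopper

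*Protocol*

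**What the plan says.** On stopping drug, Protocol 7.1 states "If the study drug is discontinued, then the participant will early exit from the study". SAP 6.2.3 repeats it: "The participant will be exited from the study after discontinuation from the study treatment". Protocol 7.2 adds that "the procedures outlined for the Exit visit should be performed at the last visit the participant attends". SAP 6.2.3 treats the safety assessment at that exit as the last one of the treatment period.

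On the end of event collection, Protocol 8.3.7 has AE and SAE collection "continue until the last day of study participation (D84", with the bracket closing there, and SAP 3.7 says the same. Events already open are followed for 7 days (non-serious) or 30 days (serious) beyond that point. For a termination in the first 4 weeks, Protocol 8.3.9 says "the occurrence of an SAE within 8 weeks from Baseline/Day 1 should be reported immediately".

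Protocol 6.4, in its paragraph on people enrolled despite a significant eligibility deviation and then discontinued, says "Participants will be scheduled for follow-up visits and followed for 8 weeks post-treatment for safety per protocol".

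The safety population (SAP 5.2) keeps everyone randomized who took a dose. SAP 4.7.1 plans a separate tabulation of AEs that start more than 3 days after the last dose.

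**The concern.** Protocol 7.1 names a safety concern as the reason for which an investigator may stop drug. Those participants are the ones whose course off drug is most informative, yet the plan ends their scheduled contact at the exit assessment. A completer is seen twice off drug. A wrongly enrolled participant is offered 8 weeks of post-treatment safety visits. Someone stopped for, say, a troublesome but non-serious ocular reaction gets neither.

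Protocol 2.2 calls this the first clinical study of the topical product, so there is little other human information on what follows withdrawal of the drops. The same people also stay in the denominator of the post-treatment AE table, although nobody is scheduled to ask them about events in that period.

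**Working it through.** **1. The plan's own figures.** Treatment of 4 weeks plus 8 weeks off drug is 28 + 56 = 84 days, which agrees with the Day 84 exit visit. The drop-out allowance is 70 − 60 = 10, and 10/70 = 14.3%. How many of those 10 would be drug stops is not stated. Protocol 2.2 mentions no drug stop among the first 24 dosed.

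**2. Scheduled off-drug safety contact, by type of participant.**

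| Participant | Scheduled after the last dose | Source |
|---|---|---|
| Completer | 2 visits, Days 56 and 84 | Protocol 1.3 |
| Wrongly enrolled, then discontinued | Visits over 8 weeks post-treatment | Protocol 6.4 |
| Stopped for a drug-related SAE | Monitoring of that SAE, about 30 days or more | Protocol 7.1, 8.3.9 |
| Any other early stopper | Exit procedures, then 0 contacts | Protocol 7.1, 7.2; SAP 6.2.3 |

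**3. Would an existing safeguard find a new event in the last row?**
- Outcome follow-up of 7 or 30 days (8.3.7) starts from an event already open.
- Liver retesting (8.3.11) starts from a raised ALT or AST.
- Unscheduled visits (8.2) start from a concern that has already arisen.
- The 8-week SAE clause (8.3.9) makes a new SAE reportable, but the site must first hear of it, and no call or visit is planned.

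None of them asks about a new non-serious AE.

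**4. The SAE end date.** 8 weeks from Day 1 is 8 × 7 = 56, about Day 56. For a last dose on day s, the off-drug days to Day 84 are 84 − s, and the part within the 8-week clause is 56 − s.

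| Last dose | To Day 84 | Within the 8-week clause | Share |
|---|---|---|---|
| Day 1 | 83 | 55 | 66% |
| Day 7 | 77 | 49 | 64% |
| Day 14 | 70 | 42 | 60% |
| Day 21 | 63 | 35 | 56% |

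The part outside the clause is 84 − 56 = 28 days in every row. Whether it lies inside or outside the collection period depends on what the last day of participation means for someone who has exited, and 8.3.7 does not say.

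**5. The post-treatment AE table.** Treatment-emergent events run to 3 days after the last dose (SAP 4.7). For a completer, the rest of the period is Days 32 to 84: 84 − 31 = 53 days, with 2 contacts. For an assumed stop on Day 12 it is Days 16 to 84: 84 − 15 = 69 days, with 0 contacts.

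**6. Possible between-arm bias (assumed inputs).** Take 23 per arm, 5 stops on active and 1 on vehicle, the same true post-treatment AE risk p in both arms, and no post-exit event captured in stoppers. The expected number of participants with a recorded event is p × (23 − k), where k is the number of stops.
- p = 10%: 1.8 vs 2.2, difference 0.4
- p = 20%: 3.6 vs 4.4, difference 0.8
- p = 30%: 5.4 vs 6.6, difference 1.2

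For SAEs, assume a 5% risk spread evenly over 84 days, with every SAE up to Day 56 reported for stoppers. The recorded percentage is [(23 − k) × 0.05 + k × 0.05 × 56/84] / 23.
- k = 5: 1.067/23 = 4.64%
- k = 1: 1.133/23 = 4.93%
- Difference: 1.133 − 1.067 = 0.07 participant

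With equal numbers of stops in the arms, both differences are 0.

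**The case against.** A reader might infer that Protocol 8.3.9 cuts SAE reporting off at 8 weeks and so contradicts the Day 84 in 8.3.7 by 28 days. The documents do not establish that. The 8-week clause covers only terminations in the first 4 weeks. SAP 7.2 sets the last date in study as the Day 84 visit or else the last visit at which the investigator saw the participant. On that definition an early stopper's participation ends at exit, and 8.3.9 lengthens SAE reporting rather than shortening it. What remains is ambiguity: a site cannot tell from 8.3.7 which end date applies.

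A reader might also infer that early stoppers have no safety follow-up at all. That goes too far. Drug-related SAEs, open events, liver signals and SAEs to about Day 56 are provided for, and SAP 3.1.4 includes an Early Discontinuation visit with laboratory tests, ECG and dilated fundus examination. The gap is narrower: active detection of new events after that visit.

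The sentence in 6.4 on 8 weeks of follow-up could be read as covering every discontinued participant. It stands in the paragraph on wrong enrolment, however, and a general reading would contradict 7.1.

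The conjunctival staining described in Protocol 2.2, which resolved 2 months after treatment ended, is not an example of a missed new event. It began on treatment and was already known. It shows that effects can persist off drug, no more.

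Finally, the number of drug stops is unknown and may be very small, and the efficacy analysis and power are untouched. That stands, and it limits the weight of the point.

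**Conclusion.** The point holds as a gap in safety follow-up. An ordinary early stopper gets one exit assessment and then 0 scheduled contacts, against 2 off-drug visits for a completer. New non-serious AEs after exit are not actively collected. SAE capture after exit is passive and runs to about Day 56 rather than Day 84, with the intended end date unclear.

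It is not a threat to the main safety comparison. SAP 6.6 rests mainly on treatment-emergent AEs, whose window closes 3 days after the last dose for everyone. At most, an exit visit on the day of the last dose leaves those 3 days unasked. A reader might infer material bias between arms. The figures do not support it: the illustration gives 0.4 to 1.2 participants in the post-treatment table and under 0.1 for SAEs, needs unequal stops, and uses stop counts and risks that the documents do not supply. The number of people affected is likewise not given; the only bound is the allowance of 10 drop-outs in 70. The improvement is worth making because it is cheap and this is the product's first clinical study.

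**What to change.** 1. **Protocol 7.1 and SAP 6.2.3.** Replace the forced exit with: *A participant who stops study drug has the Exit procedures at that time and is then followed for safety only, by telephone or clinic AE contact at each remaining scheduled time through Day 84, unless consent is withdrawn.* State that nothing collected after the exit visit enters the mITT analysis and that the mapping of the exit visit is unchanged.
2. **Protocol 8.3.7 and 8.3.9, and SAP 3.7.** Give one end date for AE and SAE collection: Day 84, whether or not study drug was stopped early.
3. **SAP 4.1.** Class drug stoppers as treatment discontinued even if they have a Day 84 contact. The present rule counts anyone who completes the Day 84 visit as a study completer.
4. **SAP 7.2.** For these participants, let the last safety contact set the end of AE observation. The present rule does not let contact after the final visit extend time in study. Until this is changed, a table of AEs per person-day would have no defined denominator and should not be added.

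The cost is wording plus contacts. A stop after Day 7 needs 3 (Days 28, 56 and 84), and a stop before Day 7 needs 4. If all 10 allowed drop-outs were drug stops, that is 10 × 3 = 30 to 10 × 4 = 40 contacts. All can be telephone calls, which the protocol already accepts for Day 7.
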